14.1. Subject Disposition

The number and proportion of subjects in Groups A & B eligible for and compliant with all follow-up examinations will be presented. Subjects who withdraw from the study will be tabulated with the reasons for the withdrawal. Subjects who initiate the procedure, regardless of tolerability outcome or anesthesia effectiveness, will be encouraged to return for all follow-up assessments.

14.2. General Statistical Methods

[REDACTED]

[REDACTED]

[REDACTED]

14.3.2. Analysis Sets

14.3.2.1. Modified Intention to Treat (mITT)

The mITT analysis set includes all subjects who are randomized and in whom the lidocaine is introduced into the ear canal. Subjects who discontinue iontophoresis prior to the TM tap assessment or decline TM tap assessment will provide a pain score for the attempted procedure and will be included in the mITT. Only subjects who do not complete the procedure due to reasons not related to iontophoresis discomfort (eg, anatomy not compatible with device fit) will be excluded. Subjects will be analyzed as randomized.

14.3.2.2. Per Protocol Set

The Per Protocol Set is a subset of the mITT and includes all mITT subjects without major protocol deviations. Major protocol deviations include:

- Eligibility violations
- Procedural deviations with the potential to affect anesthesia efficacy (eg, abbreviation of iontophoresis or use of incorrect local anesthesia drug).

14.3.2.3. Safety Analysis Set

The Safety Analysis Set will include all subjects in whom the lidocaine solution is introduced into the ear canal (same as the mITT set).

14.3.3. Primary Endpoint Analysis

Group A subjects are randomized to either active lidocaine iontophoresis or sham lidocaine iontophoresis. Each subject will have a VAS score.

The null and alternative hypotheses are:

$$H_0 : \mu_T - \mu_S = 0$$

vs.

$$H_1 : \mu_T - \mu_S < 0$$

where μ_T and μ_S are the mean scores in the treatment and sham arms respectively.

The primary endpoint will be evaluated in the mITT set using a permutation test at a 2.5% significance level. The primary endpoint will be demonstrated if the p-value from the permutation test is less than or equal to 0.025.

14.3.4. Safety Analysis

All reported or observed adverse events that occur for subjects in the Safety Analysis Set during or after the procedure will be recorded. All AEs will be tabulated by treatment group. AEs will be summarized by preferred terms and system organ class using the Medical Dictionary for Regulatory Activities (MedRA). The frequency of each event will be summarized by seriousness, severity and by relationship to the study device, procedure and/or drug. Separate summaries will be provided for SAEs and AEs related to study device, procedure and/or drug. In the event a subject reports the same event several times (eg, otalgia), the first occurrence of the worst reported case of the event will be used for the purpose of analysis.

[REDACTED]

[REDACTED]

- [REDACTED]
- [REDACTED]
- [REDACTED]
- [REDACTED]
- [REDACTED]
- [REDACTED]
- [REDACTED]

[REDACTED]

[REDACTED]

[REDACTED]

[REDACTED]

[REDACTED]

[REDACTED]

[REDACTED]

14.4. Group B – Statistical Methods

14.4.1. Analysis Sets

14.4.1.1. Full Analysis Set (FAS)

The FAS includes all subjects in whom the lidocaine solution is introduced into the ear canal.

14.4.1.2. Per Protocol Set

[REDACTED]

- [REDACTED]
- [REDACTED]
- [REDACTED]
- [REDACTED]
- [REDACTED]
- [REDACTED]
- [REDACTED]

[REDACTED]

[REDACTED]

[REDACTED]

[REDACTED]

[REDACTED]

- [REDACTED]
- [REDACTED]
- [REDACTED]
- [REDACTED]
- [REDACTED]

[REDACTED]

[REDACTED]

[REDACTED]

[REDACTED]

[REDACTED]

[REDACTED]

[REDACTED]

[REDACTED]

[REDACTED]

[REDACTED]

[REDACTED]

[REDACTED]

[REDACTED]

[REDACTED]

[REDACTED]

[REDACTED]

[REDACTED]

[REDACTED]

14.6. Handling Drop Outs or Missing Data

Group A Primary Endpoint: If a subject in Group A discontinues iontophoresis prior to the TM tap assessment or declines TM tap assessments, the subject will provide a VAS pain score for the attempted procedure and will be included in the analysis of the primary endpoint. [REDACTED]

[REDACTED]

[REDACTED] Reasons for discontinuation will be documented and presented in the clinical study report.

Group B Primary Endpoint: If a subject in Group B discontinues iontophoresis or tube placement, the subject will provide a VAS pain score for the attempted procedure. Subjects with discontinued procedures will be included in the sensitivity analyses only, and will not be included in the primary analysis. Only subjects with scores after tubes are successfully placed in all indicated ears (one tube if indicated for unilateral treatment and two tubes if indicated for bilateral treatment) will be included in the primary analysis. [REDACTED]

[REDACTED]

[REDACTED] Reasons for discontinuation will be documented and presented in the clinical study report.

[REDACTED]

[REDACTED]

14.7. Multiplicity Adjustment

Groups A & B each have a single primary endpoint tested at a significance level of 2.5%. Each primary endpoint must pass the statistical test for the study to be considered successful. The familywise error rate is therefore controlled at 2.5% and no multiplicity adjustments are planned.

15.0 ETHICS/PROTECTION OF HUMAN SUBJECTS

Prior to enrolling subjects, all sites must have the approval of an Institutional Review Board (IRB) responsible for reviewing clinical studies at the study site. The IRB must also approve the subject Informed Consent as well as recruiting advertisements and subject-facing information. Amendments to any of these documents must also be approved by the IRB. No subjects will be consented or enrolled to a site until IRB approval has been received in writing. The Informed Consent process is described in **Section 12.3**.

15.1. Subject Confidentiality

Subject confidentiality will be maintained at all times during the study. A unique subject identifier will consist of (1) a Protocol Identifier, (2) an Investigational Site identifier, and (3) a consecutive subject number with designated group assignment (A or B).

Example: 7003-JON-A01 in Group A

7003 = 4 digit Protocol Number

JON = Investigator [name]

A01 = Number of subject enrolled

The Investigator or evaluation personnel at each study site will assign the subject identifier and access to this identifier will be restricted to the Investigator and evaluation personnel. The key to the subject identifier and subject data collection sheets containing the subject's name and identification code will be securely maintained at each study site.

16.0 PREMATURE TERMINATION OR WITHDRAWAL

16.1. Subject Stopping Criteria

Subjects who do not complete the study procedure will be encouraged to remain in the study to complete post-procedure evaluations. If a subject withdraws prematurely from the study, a genuine effort must be made to determine the reason(s) why the subject failed to return for the procedure or follow-up visit or discontinued the study, and the reason must be recorded on the appropriate CRF.

Potential reasons for discontinuation include:

- Subject decides it is in their best interest to withdraw
- Subject expresses intolerable discomfort during the procedure and indicates they wish to stop the procedure and withdraw

- Serious adverse event that requires withdrawal from the study
- Investigator decides it is in the subject's best interest to be withdrawn if subject is experiencing intolerance or intolerable reaction to the procedure.

If the subject wishes to discontinue participation in the study, the Investigator will attempt to have the subject continue participation to complete follow-up assessments unless the subject's safety is compromised. All Serious Adverse Events that have not resolved by the end of the subject's participation in the study, must be followed until the event resolves, stabilizes or becomes non-serious.

All potential subjects in the study will be verbally informed and will sign an informed consent in compliance with 21CFR §50 that states that any withdrawal from the study will neither prejudice nor in any way affect their future treatment.

Prior to designating a subject as lost to follow-up, the site must provide documented evidence of three (3) good faith attempts to contact the subject to which there has been no response. At that point the subject will be considered lost-to-follow-up and withdrawn from the study.

■ [REDACTED]

[REDACTED]
[REDACTED]
[REDACTED]

- [REDACTED]
- [REDACTED]
- [REDACTED]
- [REDACTED]

[REDACTED]
[REDACTED]

- [REDACTED]
- [REDACTED]
[REDACTED]
[REDACTED]
- [REDACTED]
[REDACTED]
- [REDACTED]
[REDACTED]

[REDACTED]

[REDACTED]

[REDACTED]

[REDACTED]

[REDACTED]

[REDACTED]

17.0 INVESTIGATOR RESPONSIBILITIES

Investigators who participate in this study will conduct the study according to the protocol, the Declaration of Helsinki, GCP and applicable regulatory requirements. Tusker Medical will sponsor the conduct of the study at up to 8 investigational centers. This study will be performed under the direction and responsibility of the physician investigator at each study site. It is the responsibility of the Investigators to ensure study material is reviewed and approved by all applicable Institutional Review Boards (IRB), hospital committees, and administrative personnel as required.

The Investigator is responsible for the execution of the study, proper performance of participating personnel, ensuring adherence to the protocol and schedule of procedures, and for the control of devices under investigation. The Investigator is also responsible for protecting the rights, safety, and welfare of subjects under the investigator's care, and ensuring that written informed consent is obtained.

The Investigator is responsible for data confidentiality, quality, and completeness, and proper data storage in a secure file for a period of time as indicated in the protocol, Clinical Trial Agreement (CTA) and if mandated, by the respective IRBs.

The Investigator and site personnel directly involved with the study will receive training in the protocol and use of devices prior to initiation of the study. This training will be conducted by the Sponsor (Tusker Medical, Inc.) or designee, prior to initiation of the study.

19.0 MONITORING

Tusker Medical, Inc. (Sponsor) or designee will monitor the study sites to ensure investigators are in compliance with the protocol; subject informed consent forms are properly completed; adequate protection of the rights of the human subjects and the quality and integrity of the resulting data; study data is verified against source documents for key safety and effectiveness variables; investigational devices and drug are properly controlled; and verification that reports are filed in accordance with the protocol and the appropriate regulations. Monitoring will be conducted according to the Sponsor’s monitoring procedure and study monitoring plan.

20.0 INVESTIGATIONAL PRODUCT ACCOUNTABILITY

Access to investigational drug and devices shall be controlled and the investigational drug and devices shall be used only in the clinical investigation and according to the protocol. The Sponsor shall keep records to document the physical location of all investigational drug and devices from shipment to the investigation sites until return or disposal. Drug and devices will be stored according to product labeling. The principal investigator or an authorized designee shall keep records documenting the receipt, use, return, and disposal of the investigational drug and devices, which shall include (a) the date of receipt, (b) identification of each investigational drug and device (batch number/serial number or unique code), (c) the expiration date, (d) the date or dates of use, (e) subject identification, and (f) the date of return of unused, expired or malfunctioning investigational products, if applicable.

21.0 DEVIATIONS

A protocol deviation is defined as any event where the Investigator or site personnel deviate from the study protocol or study procedures for any reason. It is the Investigator’s responsibility to ensure that there are no protocol deviations throughout the life of the study. In the event that a non-emergency protocol deviation is identified, at the time of identification, the personnel identifying the event will review and define appropriate

corrective actions to prevent recurrence. The IRB will be notified as applicable. Any deviations from this protocol will be documented by the site on a protocol deviation CRF.

22.0 DATA HANDLING AND RECORD KEEPING

22.1. Source Data and Case Report Forms

All study data will be captured on source documents by the Investigational Site. Data from the source documents will be recorded to CRFs by site personnel that have been trained on the protocol and CRF completion.

22.2. Data Quality Assurance

Accuracy and reliability of the clinical study data will be ensured by selection of qualified investigators, and appropriate study centers, review of protocol procedures with the investigators and associated personnel prior to the study, and by periodic monitoring visits by the sponsor. CRFs will be reviewed for accuracy and completeness by the sponsor during on site monitoring visits and after their return to the sponsor, and any discrepancies will be resolved with the investigator or designees, as appropriate.

22.3. Record Retention

All clinical sites will maintain all records pertaining to this study for a minimum of two years after marketing approval or formal discontinuation of investigational product development. The Sponsor will notify the clinical sites of the date of discontinuation. No study-related records, written or electronic, will be destroyed or transferred without specific written approval by the Sponsor.

23.0 PUBLICATION POLICY

The CTA mutually signed by the Investigator(s) and Tusker Medical, Inc., defines and describes the nature of the study agreement.

The Sponsor retains the rights to this protocol and the CRFs before and after data entry. Tusker Medical, Inc. reserves the right to review any reports of this study to verify that the information is accurate and to ensure the content and timing of any such publication is mutually agreed upon by the Investigator(s) and Tusker Medical, Inc. Draft abstracts, manuscripts, and materials for presentation at scientific meetings should be provided to the sponsor at least 30 working days prior to submission.

Clinical trial information will be registered in the clinical trial registry databank maintained by the National Institutes of Health/National Library of Medicine (NIH/NLM) per FDAAA 801 requirements. If a future publication results from this study, authorship will be established according to ICMJE guidelines.

1.0 Scope

This is the Statistical Analysis Plan (SAP) for the final analysis of data collected under Protocol Number CPR007003.

2.0 Trial Objectives

The objectives of the study are two-fold:

- 1) to determine if active lidocaine iontophoresis is superior to sham lidocaine iontophoresis in providing anesthesia to the tympanic membrane, and
- 2) to evaluate tolerability and safety of tympanostomy tube (TT) placement in adults following local anesthesia in a physician's clinic setting (henceforth referred to as 'in-office').

3.0 Trial Endpoints

3.1 Co-Primary Endpoints

- **Group A-Anesthesia Effectiveness:** Subject-reported pain score elicited by tympanic membrane tap following active lidocaine iontophoresis compared to sham lidocaine iontophoresis using Visual Analogue Scale (VAS).
- **Group B -Tube Placement Tolerability:** Subject-reported pain score following TDS tube placement using the VAS by subject compared to a performance goal.

3.2 Safety Endpoint

Occurrence of adverse events, by subject (Groups A and B)

3.3 Secondary Endpoints

None.

[REDACTED]

[REDACTED]

[REDACTED]

[REDACTED]

[REDACTED]

[REDACTED]

[REDACTED]

[REDACTED]

[REDACTED]

4.0 Trial Design

This study is a prospective, multicenter evaluation of safety and effectiveness of iontophoresis and tympanostomy tube placement using the IPS and TDS for TT placement for adults in an office setting.

The study will consist of two independent Groups. Each group has their own primary endpoint, each of which must pass the statistical test for the overall study to be considered successful:

- Group A will consist of 40 evaluable healthy adult subjects aged 18-50 (inclusive), enrolled at two investigational centers in the US. Group A subjects will be randomized (1:1) to receive unilateral (1 ear) treatment with either active lidocaine iontophoresis or sham lidocaine iontophoresis. The sham iontophoresis procedure will be identical to the active lidocaine iontophoresis, with the exception that the iontophoresis channel will not be activated (ie, the same drug solution will be applied to ears in both arms). After the completion of the iontophoresis, the tympanic membrane will be tapped with a dull otologic

probe to test the level of anesthesia. The subject will rate the level of pain using the VAS, and pain scores from the active iontophoresis group will be compared to the sham iontophoresis group.

- Group B will consist of 30 evaluable adults age 18 years or greater who require unilateral or bilateral tube insertion enrolled at up to 9 centers in the US. Group B subjects will receive active lidocaine iontophoresis and will have tubes placed using the TDS in all ears indicated for tube placement. The subject will rate the pain upon TDS tube insertion using the VAS, and the pain score (by subject) is compared to a fixed performance goal.

5.0 Study Cohorts

There are two cohorts in the study:

Group A: Healthy adult volunteers randomized to active lidocaine iontophoresis or sham lidocaine iontophoresis, followed by assessment of anesthesia effectiveness.

Group B: Adults indicated for tympanostomy tube placement undergoing lidocaine iontophoresis and TDS-mediated tympanostomy tube placement, followed by assessment of tube placement tolerability.

6.0 Randomization and Blinding (Group A only)

Subjects will be randomized (1:1) to either active lidocaine iontophoresis or sham iontophoresis. Randomization will be stratified by site and will be balanced by using permuted blocks. [REDACTED]

The study will be double-blinded such that the Investigator and subjects will be blinded to treatment assignment to minimize bias regarding Investigator and Subject-reported outcomes. [REDACTED]

- [REDACTED]
- [REDACTED]
- [REDACTED]
- [REDACTED]

[REDACTED]

[REDACTED]

7.0 Analysis Sets – Group A

7.1 Group A

7.1.1 Modified Intention to Treat (mITT)

The mITT analysis set includes all subjects who are randomized and in whom the lidocaine is introduced into the ear canal. Subjects who discontinue iontophoresis prior to the TM tap assessment or decline TM tap assessment will provide a pain score for the attempted procedure and will be included in the mITT. [REDACTED]

7.1.2 Per Protocol

The Per Protocol Set is a subset of the mITT and includes all mITT subjects without major protocol deviations. Major protocol deviations include:

- Eligibility violations
- Procedural deviations with the potential to affect anesthesia efficacy (eg, abbreviation of iontophoresis or use of incorrect local anesthesia drug).

7.1.3 Safety Analysis Set

The Safety Analysis Set will include all subjects in whom the lidocaine solution is introduced into the ear canal (same as mITT set).

7.2 Group B

7.2.1 Full Analysis Set (FAS)

The FAS includes all subjects in whom the lidocaine solution is introduced into the ear canal.

7.2.2 Per Protocol Set

The Per Protocol Set is a subset of the FAS and includes FAS subjects without major protocol deviations. Major protocol deviations include:

- Eligibility violations
- Procedural deviations with the potential to affect anesthesia efficacy (eg, abbreviation of iontophoresis or use of incorrect local anesthesia drug).

7.2.3 Safety Analysis Set

The Safety Analysis Set will include all subjects in whom the lidocaine solution is introduced into the ear canal (same as FAS).

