12.5.3. Earset Sizing

The IPS Earset is available in 6 sizes. The ear sizing procedure will be performed according to the Instructions for Use (IFU) provided with the IPS. If the subject's ear is not compatible

with the ear plug and fit cannot be established to ensure the earplug can properly seal in the ear canal, the subject will be considered a screening failure.

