12.5.5. Earset Placement and Drug Instillation

Baseline tolerability will be assessed before placement of the Earset. The Earset ear plug of the size determined in the ear sizing procedure is then placed into the ear canal. Once the ear plug is positioned, the protective liner is removed, exposing the PSA to the ear canal. Circumferential pressure is applied through the ear plug against the surface of the ear canal, ensuring adhesion of the PSA. The Earset's integrated fill system is used to instill the selected drug into the ear canal. This process is repeated for the second ear, as applicable.

The Electrode Cable is snapped to the Return Electrode Patch. The Return Electrode Patch is then attached to the patient at a clean, dry site (such as the shoulder near the base of the neck) that is clear of lesions, bony protuberances and excessive hair. Prior to placing the return electrode on the patient, the investigator will assess the location for pre-existing erythema using the five point Draize erythema score where 0 indicates no erythema, 1 = very slight erythema (barely perceptible), 2 = well-defined erythema, 3= moderate to severe erythema, 4= severe erythema to slight eschar formation.⁴³ The location will be assessed again following iontophoresis.

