13.3. Adverse Event Definitions

Adverse Event (AE)

An AE is any unfavorable and unintended sign, symptom, or disease temporally associated with the procedure or use of the device or investigational drug, and does not imply judgment about causality.

Serious Adverse Event (SAE)

AEs are classified as serious or non-serious. A serious adverse event is any AE that is:

- Fatal
- Life-threatening
- Requires or prolongs hospital stay
- Results in persistent or significant incapacity or substantial disruption of the ability to conduct normal life functions
- Led to fetal distress, fetal death or congenital abnormality or birth defect

- An important medical event that may jeopardize the subject, and may require medical or surgical intervention to prevent one of the other serious outcomes noted above.

Life Threatening Adverse Event or Life-Threatening Suspected Adverse Reaction

An adverse event or suspected adverse reaction is considered life threatening if, in the view of either the investigator or sponsor, its occurrence places the subject at immediate risk of death. It does not include an adverse event that, had it occurred in a more severe form, might have caused death.

Unanticipated Adverse Device Effect (UADE)

A UADE is any serious adverse effect on health or safety or any life-threatening problem or death caused by, or associated with, a device, if that effect, problem or death was not previously identified in nature, severity, or degree of incidence in the investigational plan or application, or any other unanticipated serious problem associated with a device that relates to the rights, safety, or welfare of subjects.

In order to ensure subject safety during the study, all adverse events assessed as “serious” in the opinion of the Investigator will be reviewed by the Medical Monitor to determine any causal relationship to the study drug, device or procedure. All adverse events that do not meet any of the criteria for serious should be regarded as non-serious adverse events. Non-serious adverse events must still be documented on the appropriate CRF.

Reporting

The sponsor will notify FDA, all reviewing IRBs and all participating Investigators of potential serious risks, from this study or any other source, as soon as possible, but in no case later than 15 calendar days after the Sponsor determines that the information qualifies for reporting, including:

1. Suspected adverse drug reactions that are considered both serious and unexpected,

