14.0 Safety Endpoint Analyses

14.1 Adverse Events

Adverse events (AEs) reported during the study will be coded using the Medical Dictionary for Regulatory Activities (MedDRA). The number and percentage of subjects reporting adverse events will be summarized by MedDRA system organ class and preferred term for each Group (A and B).

The frequency of each event will be summarized by seriousness, severity and by relationship to the study device, procedure and/or drug. For all AE tables, a subject reporting the same AE more than once will be counted once when calculating the number and percentage of subjects with that particular event. If a subject reports the same AE more than once or has the same AE on multiple occasions, the maximum severity grade recorded for the event will be presented.

Overall summaries of serious and non-serious AEs will be presented. The overall summaries will include the number and percentage of patients experiencing AEs classified by treatment, relationship to device/procedure/study drug, MedDRA SOC (System Organ Class) and preferred term. Summaries of AEs will also be presented by severity for each treatment group including the number and percentage of patients

experiencing AEs classified by relationship to device/procedure/study drug, SOC and preferred term.

Safety events will be reported for all subjects in which the lidocaine solution was introduced into the ear (Safety Analysis Set) and will be reported for the following time intervals:

- Events occurring during the procedure visit
- Events occurring between the procedure through the subject's final follow-up visit

[REDACTED]

[REDACTED]

Complete patient listings of all AEs will be provided. For each AE the following will be specified: start and stop dates, severity grade and MedDRA SOC, relationship to study device, relationship to procedure, relationship to study drug, action taken, outcome of the adverse event and seriousness, where appropriate. Any unanticipated adverse events will be noted.

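### The Safety Analysis Set starts at lidocaine instillation, so a subject stopped by an event during Earset placement is missing from the adverse-event tables

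*SAP*

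**What the plan says.** The only safety endpoint is the occurrence of adverse events by subject in Groups A and B (SAP 3.2). The set on which it is analysed is defined by the drug:

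- Group A, SAP 7.1.3: "The Safety Analysis Set will include all subjects in whom the lidocaine solution is introduced into the ear canal (same as mITT set". Protocol 14.3.2.3 agrees: "The Safety Analysis Set will include all subjects in whom the lidocaine solution is introduced into the ear canal (same as the mITT set".
- Group B, SAP 7.2.3: "The Safety Analysis Set will include all subjects in whom the lidocaine solution is introduced into the ear canal (same as FAS". The corresponding Protocol section (14.4.1.3) is not visible in the public text.
- Reporting, SAP 14.1: "Safety events will be reported for all subjects in which the lidocaine solution was introduced into the ear (Safety Analysis Set". Protocol 14.3.4 (Group A) uses the same population: "All reported or observed adverse events that occur for subjects in the Safety Analysis Set during or after the procedure will be recorded".

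The adverse-event definition is wider. Protocol 13.3 covers any unfavourable sign, symptom or disease "temporally associated with the procedure or use of the device or investigational drug".

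Protocol 12.5.5 gives the order of steps. The Earset plug goes into the canal, its liner is removed, and then: "Circumferential pressure is applied through the ear plug against the surface of the ear canal, ensuring adhesion of the PSA". The drug is instilled afterwards, through the Earset already in place.

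**The concern.** The trial evaluates devices together with a drug, and the Earset is one of the three components of the Iontophoresis System (Protocol 7.1.1). Exposure to it begins before exposure to lidocaine, but entry to the safety set waits for the lidocaine.

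A subject who has canal pain, abrasion or bleeding as the plug is seated, and who stops for that reason, has had an adverse event under Protocol 13.3. That subject is nevertheless outside the set on which adverse events are tabulated. The exclusion is informative, because the event itself keeps the subject out. A similar event that does not stop the procedure is counted.

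At stake is whether the AE tables give the right numerator and denominator for events related to Earset placement. Within this gap the error can only understate such events.

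**Working it through.** The point is definitional, and the plan states no figure that needs reproducing. The check sets the rules side by side and then illustrates the size.

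1. **Entry to the set.** Lidocaine in the ear canal, both Groups (SAP 7.1.3, 7.2.3; Protocol 14.3.2.3 for Group A).
2. **First contact with the study device during treatment.** Placement of the Earset plug, then liner removal and circumferential pressure, all before instillation (Protocol 12.5.5; same order in 7.1.2).
3. **What counts as an adverse event.** Device use as well as drug use (Protocol 13.3). SAP 14.1 also classifies events by relationship to device, procedure and drug.
4. **Three cases under these rules.**
   - Canal abrasion at placement, procedure continues to instillation: in the set, counted.
   - Abrasion at placement, noticed only after instillation: in the set, counted.
   - Abrasion at placement, subject stops before instillation: not in the set, not in the AE tables.

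   The third case differs from the first only in that the subject stopped.
5. **Where the third case still appears.** Protocol 13.1 records events during or after the procedure without limiting them to an analysis set. SAP 22.0 lists eCRF data for all enrolled subjects. SAP 8.0 tabulates screen failures and discontinuations with reasons. So the event is in the data but not in the endpoint tables.
6. **The stated equivalence in Group A.** The safety set is everyone instilled, and is also said to equal the mITT set. Protocol 14.3.2.1 removes from mITT those who do not complete the procedure for reasons unrelated to iontophoresis discomfort. A subject instilled and then stopped for such a reason is in the safety set by its definition and out of it by the equivalence. Both statements cannot hold.
7. **Illustration of size.** The documents give no count of subjects stopped between placement and instillation. Assume x such subjects (range 0 to 3 in Group B, 0 to 1 in Group A), each with one Earset event, no other such event, and n instilled subjects equal to the evaluable targets of 30 (Group B) and 40 (Group A). The current set reports 0/n. A set starting at placement reports x/(n + x). Limits are exact two-sided 95% (Clopper-Pearson). For x = 0 the upper limit is 1 − 0.025^(1/n), which for n = 30 is 11.6%.

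| Group | x | Set starting at placement | 95% limits |
|---|---|---|---|
| B | 0 | 0/30 = 0% | 0 to 11.6% |
| B | 1 | 1/31 = 3.2% | 0.1 to 16.7% |
| B | 2 | 2/32 = 6.3% | 0.8 to 20.8% |
| B | 3 | 3/33 = 9.1% | 1.9 to 24.3% |
| A | 0 | 0/40 = 0% | 0 to 8.8% |
| A | 1 | 1/41 = 2.4% | 0.1 to 12.9% |

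   Whatever x is, the current set reports the x = 0 row. The visible text plans no confidence limits for AE rates; they are shown only to indicate precision. The Group B safety set includes instilled non-completers, so it may exceed 30, and the shift would then be slightly smaller.

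**The case against.** The strongest reply is that little is lost. Most Earset exposure comes after instillation: about 10 minutes of current with the plug in place, then peeling it off. Events from those steps are in the set, as are placement injuries in anyone who goes on to receive drug. For the rest, besides recording, listing and disposition, SAP 10.0 summarises procedure and device performance by Group with no stated restriction to the safety set. Protocol 13.6 records device malfunctions with their timing and any related adverse event, and 13.5 has ear-related events reviewed within 24 hours of sponsor awareness. All of this stands, and it confines the gap to the AE frequency tables and to a short interval. It does not close the gap, because none of these outputs is the safety endpoint's numerator or denominator.

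A reader might infer more than the documents support:

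- **That such events disappear, or survive only in a listing.** The outputs just named show otherwise.
- **That the most severe Earset events are lost and device risk is driven toward zero.** Nothing in the documents ranks events before instillation as the most severe, and most Earset exposure is inside the set. Sham and active subjects in Group A follow the same steps up to activation, so no bias between arms is expected either.
- **That an injured subject would be relabelled a screening failure.** Protocol 12.5.3 concerns fit: when "fit cannot be established to ensure the earplug can properly seal in the ear canal, the subject will be considered a screening failure". It does not address injury during placement.
- **That a pooled rate over 70 subjects, or the roughly 15 non-evaluable subjects of 85, measures the effect.** The 70 is an evaluable count, AE tables are by Group, and the 15 are screen failures or withdrawals for any reason (Protocol 11.4).

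**Conclusion.** The concern holds in a narrow form. As written, a subject who stops between Earset placement and instillation because of an Earset-related event is left out of the AE frequency tables for the safety endpoint, and is left out because of that event. The event remains in the data, so the defect is confined to the analysed set.

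Its size is unknown. If no subject stops in that interval for such an event, the AE tables are unaffected. One such subject in Group B would move the rate from 0/30 to 1/31 (3.2%), under the assumptions that no other such event occurs and that exactly 30 subjects are instilled. With groups this small, one subject alters the safety statement, so the set is worth correcting before analysis.

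For Group A the finding rests on both documents. For Group B it rests on the SAP alone. Part of SAP 14.1 is also redacted.

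**What to change.** - In SAP 7.1.3 and 7.2.3 and Protocol 14.3.2.3, define the Safety Analysis Set as all subjects in whom placement of an Earset in the ear canal was started or study drug was introduced, whether or not lidocaine was instilled. Check the Protocol's Group B section for the same wording.
- Delete the statements that the set is the same as the mITT set (Group A) and the FAS (Group B). This also removes the Group A conflict with Protocol 14.3.2.1.
- Align the reporting sentence in SAP 14.1 with the new set.
- Leave the mITT and FAS definitions unchanged, so the efficacy analyses and power are untouched.
- Report any adverse event during Earset sizing separately, among screen failures. Starting the set at sizing would bring uninjured fit failures into the denominator and could dilute AE rates.

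The cost is a wording change in two documents, a few more subjects in the safety tables and possibly a slightly less favourable AE rate.
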